12.6 Public disclosure and publication policy

All papers and abstracts will be co-authored by the study coordinators and by one investigator from each centre that has contributed one or more patients to the data to be analysed. Full articles on the clinical topics to the study will be prepared by the

study coordinator(s) and will also be co-authored by the statistician and possibly by the data manager. Presentations at national or international meetings may be given by investigators from individual centres, but will require the approval of the study coordinators prior to submission in all cases. These rules will apply exclusively to publications and/or presentations of data that have been collected among more than a single centre. Investigators remain free to report in any desired form on patients treated exclusively in their own centre.

This trial will be registered at www.trialregister.nl/

13. STRUCTURED RISK ANALYSIS

13.1 Potential issues of concern

Risk of groin recurrence: There is a risk that SLN procedure will not be as effective as full IFL. But there are sufficient data that support the feasibility of SLN in the first recurrence in vulvar cancer.

In breast cancer, repeat SLN is feasible and provides reliable results(12). There are no arguments why vulvar cancer should have different outcomes than breast cancer. In our retrospective study, in 2 out of 27 patients, the SLN was located outside the surgical margins of the normal IFL, possibly due to an aberrant drainage pattern(11). These patients will not profit from a full IFL.

Since it is not guaranteed that a repeat SLN procedure is as safe as a primary SLN procedure, we have a stopping rule and a Safety Committee installed.

a. Level of knowledge about mechanism of action

Not applicable.

b. Previous exposure of human beings with the test product(s) and/or products with a similar biological mechanism

Not applicable.

c. Can the primary or secondary mechanism be induced in animals and/or in *ex-vivo* human cell material?

Not applicable.

d. Selectivity of the mechanism to target tissue in animals and/or human beings

Not applicable.

e. Analysis of potential effect

Not applicable.

f. Pharmacokinetic considerations

Not applicable.

g. Study population

Not applicable.

h. Interaction with other products

Not applicable.

i. Predictability of effect

Not applicable.

j. Can effects be managed?

Not applicable.

13.2 Synthesis

Since the majority of patients with recurrent vulvar cancer are frail, an observational study of accuracy, in which a SLN biopsy and an IFL are done during the same surgical procedure and in which the accuracy of the SLN is confirmed in the IFL is not feasible: too many frail women will refuse this extensive surgery.

In general, little information is available on groin recurrences and outcome of treatment in recurrent vulvar cancer. To reduce the knowledge gap we will ask all patients for either the non- SLN cohort (observational study) (in case an IFL is done because of a proven groin metastases) or the V2SLN study as described with the possibility for the patient to choose for a SLN procedure (or not).

Appendix 1: Stopping rules

The predictive probability design for phase II cancer clinical trial as described by Lee and Liu was used to develop the stopping rule for this study. (20) This method has the advantage over two and three stage designs that the safety can be monitored constantly rather than at a pre-specified fixed number of patients.

Under the hypothesis testing framework, this clinical trial is designed to test

$$H_0 : p \leq p_0$$

against

$$H_1 : p \geq p_1$$

where p represents the success rate of the SLN procedure, so that $1 - p$ is the failure rate. p_1 is the target success rate and p_0 is the minimally acceptable success rate. We consider a failure rate of SLN of 8% (i.e. $1 - p_1$) to be maximally acceptable, and our target failure rate (i.e. $1 - p_0$) is 3%. The study is designed such that $P(\text{Accept New Treatment}|H_0) \leq \alpha$, and $P(\text{Reject New Treatment}|H_1) \leq \beta$, where the maximum type I error α and the maximum type II error rate β are both set to 0.10.

In this model, we calculate PP continuously after 10 patients (i.e., with cohort size of 1) to monitor the treatment safety.

The stopping rule is based on the predictive probability (PP) of concluding a positive result by the end of the trial based on the cumulative information in the current stage. In this model, we calculate PP continuously after 10 patients (i.e., with cohort size of 1) to monitor the treatment safety. The trial is stopped when the PP drops below the lower bound ϑ_l , where ϑ_l is a parameter that is optimized by the method. The method of Lee and Liu also includes an option for early stopping of the trial in case the PP is very close to 1, using an upper bound ϑ_u . However, we did not utilize this option, since we do not expect to have to stop the trial in case the SLN procedure has a lower groin failure rate than IFL.

In the Bayesian predictive probability approach, we assume that the failure rate ($1 - p$) has a prior distribution of Beta (0.2; 0.8), which has a prior mean of 20%. Using the software of Lee and Liu (see

<https://biostatistics.mdanderson.org/SoftwareDownload/SingleSoftware/Index/84>) we calculated the minimum number of patients to obtain sufficient power with acceptable type I error rate using a 'max power' approach. The results gave a sample size of 150 patients, with

a threshold for stopping the trial of $\vartheta_l = 0.001$. The full output of the program is given below, and Figure 3 shows the stopping rule graphically.

[figure not shown]

Figure 3 Activation of stopping rule; number of groin recurrences in relation to patients with negative SLN

Program output

Input Data

```
=====
10  Nmin
1  Cohort
150  Nmax
0.0010  theta_Lbegin
0.1000  theta_Lend
0.0050  theta_Lstep
1.0000  theta_Upper
0.8000  theta_Tbegin
0.9500  theta_Tend
0.0100  theta_Tstep
0.9200  p_0
0.9700  p_1
0.8000  Prior a0
0.2000  Prior b0
0.1000  Type I Error
0.9000  Power
```

Calculation Result

=====
Parameter selection: Maximize Power.

Theta_L and theta_T ranges:

Theta_L 0.0010 0.0010

Theta_T 0.9100 0.9500

Null Case

=====
Pat.No. Rej. Reg. Rej. Reg. Prob./(p0) Prob./(p0) Prob. Cont./(p0)
(Negative) (Positive) (Negative) (Positive)

10	6	11	0.0058	0.0000	0.9942
11	7	12	0.0027	0.0000	0.9915
12	8	13	0.0035	0.0000	0.9880
13	9	14	0.0043	0.0000	0.9837
14	10	15	0.0051	0.0000	0.9786
15	10	16	0.0000	0.0000	0.9786
16	11	17	0.0005	0.0000	0.9782
17	12	18	0.0010	0.0000	0.9772
18	13	19	0.0015	0.0000	0.9757
19	14	20	0.0021	0.0000	0.9736
20	15	21	0.0027	0.0000	0.9709
21	16	22	0.0033	0.0000	0.9675
22	17	23	0.0040	0.0000	0.9636
23	18	24	0.0046	0.0000	0.9590
24	19	25	0.0053	0.0000	0.9537
25	19	26	0.0000	0.0000	0.9537
26	20	27	0.0005	0.0000	0.9532
27	21	28	0.0010	0.0000	0.9522
28	22	29	0.0015	0.0000	0.9508
29	23	30	0.0020	0.0000	0.9488
30	24	31	0.0025	0.0000	0.9463
31	25	32	0.0031	0.0000	0.9432
32	26	33	0.0036	0.0000	0.9396
33	27	34	0.0042	0.0000	0.9354
34	28	35	0.0047	0.0000	0.9307
35	29	36	0.0053	0.0000	0.9254
36	30	37	0.0058	0.0000	0.9196
37	31	38	0.0064	0.0000	0.9132
38	32	39	0.0069	0.0000	0.9063
39	33	40	0.0075	0.0000	0.8989
40	33	41	0.0000	0.0000	0.8989
41	34	42	0.0006	0.0000	0.8982
42	35	43	0.0013	0.0000	0.8969
43	36	44	0.0019	0.0000	0.8951
44	37	45	0.0025	0.0000	0.8926
45	38	46	0.0031	0.0000	0.8895
46	39	47	0.0037	0.0000	0.8858
47	40	48	0.0042	0.0000	0.8816
48	41	49	0.0048	0.0000	0.8768
49	42	50	0.0053	0.0000	0.8714
50	43	51	0.0059	0.0000	0.8656
51	44	52	0.0064	0.0000	0.8592

52	45	53	0.0069	0.0000	0.8523
53	46	54	0.0074	0.0000	0.8449
54	47	55	0.0078	0.0000	0.8371
55	48	56	0.0083	0.0000	0.8288
56	49	57	0.0087	0.0000	0.8201
57	50	58	0.0091	0.0000	0.8110
58	51	59	0.0095	0.0000	0.8015
59	52	60	0.0099	0.0000	0.7916
60	52	61	0.0000	0.0000	0.7916
61	53	62	0.0008	0.0000	0.7908
62	54	63	0.0016	0.0000	0.7892
63	55	64	0.0023	0.0000	0.7869
64	56	65	0.0030	0.0000	0.7838
65	57	66	0.0037	0.0000	0.7801
66	58	67	0.0043	0.0000	0.7758
67	59	68	0.0049	0.0000	0.7708
68	60	69	0.0055	0.0000	0.7653
69	61	70	0.0061	0.0000	0.7593
70	62	71	0.0066	0.0000	0.7527
71	63	72	0.0070	0.0000	0.7457
72	64	73	0.0075	0.0000	0.7382
73	65	74	0.0079	0.0000	0.7302
74	66	75	0.0083	0.0000	0.7219
75	67	76	0.0087	0.0000	0.7132
76	68	77	0.0090	0.0000	0.7042
77	69	78	0.0093	0.0000	0.6949
78	70	79	0.0096	0.0000	0.6852
79	71	80	0.0099	0.0000	0.6753
80	72	81	0.0102	0.0000	0.6652
81	73	82	0.0104	0.0000	0.6548
82	74	83	0.0106	0.0000	0.6442
83	75	84	0.0108	0.0000	0.6335
84	76	85	0.0109	0.0000	0.6226
85	77	86	0.0111	0.0000	0.6115
86	78	87	0.0112	0.0000	0.6003
87	79	88	0.0113	0.0000	0.5891
88	80	89	0.0114	0.0000	0.5777
89	81	90	0.0114	0.0000	0.5663
90	82	91	0.0115	0.0000	0.5548
91	83	92	0.0115	0.0000	0.5433
92	84	93	0.0115	0.0000	0.5318
93	85	94	0.0115	0.0000	0.5202
94	86	95	0.0115	0.0000	0.5087
95	87	96	0.0115	0.0000	0.4972
96	88	97	0.0114	0.0000	0.4858
97	89	98	0.0114	0.0000	0.4744
98	90	99	0.0113	0.0000	0.4631
99	91	100	0.0113	0.0000	0.4518
100	92	101	0.0112	0.0000	0.4406
101	93	102	0.0111	0.0000	0.4296
102	94	103	0.0110	0.0000	0.4186
103	95	104	0.0109	0.0000	0.4077
104	96	105	0.0107	0.0000	0.3970
105	97	106	0.0106	0.0000	0.3863

106	98	107	0.0105	0.0000	0.3759
107	99	108	0.0103	0.0000	0.3655
108	100	109	0.0102	0.0000	0.3553
109	101	110	0.0100	0.0000	0.3453
110	102	111	0.0099	0.0000	0.3354
111	103	112	0.0097	0.0000	0.3257
112	104	113	0.0096	0.0000	0.3161
113	105	114	0.0094	0.0000	0.3067
114	106	115	0.0092	0.0000	0.2975
115	107	116	0.0090	0.0000	0.2884
116	108	117	0.0089	0.0000	0.2796
117	109	118	0.0087	0.0000	0.2709
118	110	119	0.0085	0.0000	0.2624
119	111	120	0.0083	0.0000	0.2540
120	112	121	0.0081	0.0000	0.2459
121	113	122	0.0080	0.0000	0.2379
122	114	123	0.0078	0.0000	0.2301
123	115	124	0.0076	0.0000	0.2225
124	116	125	0.0074	0.0000	0.2151
125	117	126	0.0072	0.0000	0.2079
126	118	127	0.0071	0.0000	0.2008
127	119	128	0.0069	0.0000	0.1939
128	120	129	0.0067	0.0000	0.1872
129	121	130	0.0065	0.0000	0.1807
130	122	131	0.0063	0.0000	0.1744
131	123	132	0.0062	0.0000	0.1682
132	124	133	0.0060	0.0000	0.1622
133	125	134	0.0058	0.0000	0.1563
134	126	135	0.0057	0.0000	0.1507
135	127	136	0.0055	0.0000	0.1452
136	128	137	0.0053	0.0000	0.1398
137	129	138	0.0052	0.0000	0.1346
138	130	139	0.0050	0.0000	0.1296
139	131	140	0.0049	0.0000	0.1247
140	132	141	0.0047	0.0000	0.1200
141	133	142	0.0046	0.0000	0.1154
142	134	143	0.0044	0.0000	0.1110
143	135	144	0.0043	0.0000	0.1067
144	136	145	0.0041	0.0000	0.1026
145	137	146	0.0040	0.0000	0.0986
146	138	147	0.0039	0.0000	0.0947
147	139	148	0.0037	0.0000	0.0909
148	140	149	0.0036	0.0000	0.0873
149	141	150	0.0035	0.0000	0.0838
150	142	151	0.0034	0.0805	0.0000

=====
Sum: 0.9195 0.0805

PET (PP<Theta_L)/(p0): 0.9162
 PET (PP>Theta_U)/(p0): 0.0000
 PET Total /(p0): 0.9162
 E(N|p0): 93.4786

Alternative Case

Pat.No.	Rej. Reg. (Negative)	Rej. Reg. (Positive)	Prob./(p1) (Negative)	Prob./(p1) (Positive)	Prob. Cont./ (p0)
10	6	11	0.0001	0.0000	0.9999
11	7	12	0.0001	0.0000	0.9998
12	8	13	0.0001	0.0000	0.9997
13	9	14	0.0001	0.0000	0.9995
14	10	15	0.0002	0.0000	0.9994
15	10	16	0.0000	0.0000	0.9994
16	11	17	0.0000	0.0000	0.9994
17	12	18	0.0000	0.0000	0.9993
18	13	19	0.0000	0.0000	0.9993
19	14	20	0.0000	0.0000	0.9993
20	15	21	0.0000	0.0000	0.9992
21	16	22	0.0001	0.0000	0.9992
22	17	23	0.0001	0.0000	0.9991
23	18	24	0.0001	0.0000	0.9990
24	19	25	0.0001	0.0000	0.9989
25	19	26	0.0000	0.0000	0.9989
26	20	27	0.0000	0.0000	0.9989
27	21	28	0.0000	0.0000	0.9989
28	22	29	0.0000	0.0000	0.9989
29	23	30	0.0000	0.0000	0.9989
30	24	31	0.0000	0.0000	0.9988
31	25	32	0.0000	0.0000	0.9988
32	26	33	0.0000	0.0000	0.9988
33	27	34	0.0000	0.0000	0.9987
34	28	35	0.0001	0.0000	0.9987
35	29	36	0.0001	0.0000	0.9986
36	30	37	0.0001	0.0000	0.9985
37	31	38	0.0001	0.0000	0.9984
38	32	39	0.0001	0.0000	0.9983
39	33	40	0.0001	0.0000	0.9982
40	33	41	0.0000	0.0000	0.9982
41	34	42	0.0000	0.0000	0.9982
42	35	43	0.0000	0.0000	0.9982
43	36	44	0.0000	0.0000	0.9982
44	37	45	0.0000	0.0000	0.9982
45	38	46	0.0000	0.0000	0.9981
46	39	47	0.0000	0.0000	0.9981
47	40	48	0.0000	0.0000	0.9981
48	41	49	0.0000	0.0000	0.9980
49	42	50	0.0001	0.0000	0.9980
50	43	51	0.0001	0.0000	0.9979
51	44	52	0.0001	0.0000	0.9979
52	45	53	0.0001	0.0000	0.9978
53	46	54	0.0001	0.0000	0.9977
54	47	55	0.0001	0.0000	0.9976
55	48	56	0.0001	0.0000	0.9975
56	49	57	0.0001	0.0000	0.9974
57	50	58	0.0001	0.0000	0.9972
58	51	59	0.0001	0.0000	0.9971
59	52	60	0.0002	0.0000	0.9969

60	52	61	0.0000	0.0000	0.9969
61	53	62	0.0000	0.0000	0.9969
62	54	63	0.0000	0.0000	0.9969
63	55	64	0.0000	0.0000	0.9969
64	56	65	0.0000	0.0000	0.9969
65	57	66	0.0000	0.0000	0.9968
66	58	67	0.0000	0.0000	0.9968
67	59	68	0.0000	0.0000	0.9967
68	60	69	0.0001	0.0000	0.9967
69	61	70	0.0001	0.0000	0.9966
70	62	71	0.0001	0.0000	0.9966
71	63	72	0.0001	0.0000	0.9965
72	64	73	0.0001	0.0000	0.9964
73	65	74	0.0001	0.0000	0.9963
74	66	75	0.0001	0.0000	0.9962
75	67	76	0.0001	0.0000	0.9961
76	68	77	0.0001	0.0000	0.9960
77	69	78	0.0001	0.0000	0.9958
78	70	79	0.0002	0.0000	0.9957
79	71	80	0.0002	0.0000	0.9955
80	72	81	0.0002	0.0000	0.9953
81	73	82	0.0002	0.0000	0.9951
82	74	83	0.0002	0.0000	0.9949
83	75	84	0.0002	0.0000	0.9947
84	76	85	0.0002	0.0000	0.9945
85	77	86	0.0003	0.0000	0.9942
86	78	87	0.0003	0.0000	0.9939
87	79	88	0.0003	0.0000	0.9936
88	80	89	0.0003	0.0000	0.9933
89	81	90	0.0003	0.0000	0.9930
90	82	91	0.0003	0.0000	0.9927
91	83	92	0.0004	0.0000	0.9923
92	84	93	0.0004	0.0000	0.9919
93	85	94	0.0004	0.0000	0.9915
94	86	95	0.0004	0.0000	0.9911
95	87	96	0.0004	0.0000	0.9906
96	88	97	0.0005	0.0000	0.9902
97	89	98	0.0005	0.0000	0.9897
98	90	99	0.0005	0.0000	0.9892
99	91	100	0.0005	0.0000	0.9886
100	92	101	0.0006	0.0000	0.9880
101	93	102	0.0006	0.0000	0.9874
102	94	103	0.0006	0.0000	0.9868
103	95	104	0.0006	0.0000	0.9862
104	96	105	0.0007	0.0000	0.9855
105	97	106	0.0007	0.0000	0.9848
106	98	107	0.0007	0.0000	0.9841
107	99	108	0.0008	0.0000	0.9833
108	100	109	0.0008	0.0000	0.9825
109	101	110	0.0008	0.0000	0.9817
110	102	111	0.0009	0.0000	0.9808
111	103	112	0.0009	0.0000	0.9799
112	104	113	0.0009	0.0000	0.9790
113	105	114	0.0010	0.0000	0.9781

114	106	115	0.0010	0.0000	0.9771
115	107	116	0.0010	0.0000	0.9761
116	108	117	0.0011	0.0000	0.9750
117	109	118	0.0011	0.0000	0.9739
118	110	119	0.0011	0.0000	0.9728
119	111	120	0.0012	0.0000	0.9716
120	112	121	0.0012	0.0000	0.9704
121	113	122	0.0012	0.0000	0.9692
122	114	123	0.0013	0.0000	0.9679
123	115	124	0.0013	0.0000	0.9666
124	116	125	0.0013	0.0000	0.9653
125	117	126	0.0014	0.0000	0.9639
126	118	127	0.0014	0.0000	0.9625
127	119	128	0.0015	0.0000	0.9610
128	120	129	0.0015	0.0000	0.9595
129	121	130	0.0015	0.0000	0.9580
130	122	131	0.0016	0.0000	0.9564
131	123	132	0.0016	0.0000	0.9548
132	124	133	0.0017	0.0000	0.9531
133	125	134	0.0017	0.0000	0.9514
134	126	135	0.0017	0.0000	0.9497
135	127	136	0.0018	0.0000	0.9479
136	128	137	0.0018	0.0000	0.9461
137	129	138	0.0019	0.0000	0.9442
138	130	139	0.0019	0.0000	0.9423
139	131	140	0.0020	0.0000	0.9403
140	132	141	0.0020	0.0000	0.9383
141	133	142	0.0020	0.0000	0.9363
142	134	143	0.0021	0.0000	0.9342
143	135	144	0.0021	0.0000	0.9321
144	136	145	0.0022	0.0000	0.9299
145	137	146	0.0022	0.0000	0.9277
146	138	147	0.0023	0.0000	0.9255
147	139	148	0.0023	0.0000	0.9232
148	140	149	0.0023	0.0000	0.9208
149	141	150	0.0024	0.0000	0.9184
150	142	151	0.0024	0.9160	0.0000

=====

Sum: 0.0840 0.9160

PET (PP<Theta_L)/(p1): 0.0816
PET (PP>Theta_U)/(p1): 0.0000
PET Total /(p1): 0.0816
E(N|p1): 147.7381

Alpha: 0.0805
Beta: 0.0840

Predictive Probability Program PID-535
8/7/2019 6:18:48 PM

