4.4 Sample size calculation

Approximately 18% of women will have groin metastases at the moment of their first vulvar cancer recurrence. Of these, approximately 20% will be detected prior to surgery (based on imaging and FNA) and these women will not be offered a SLN procedure, but advised to undergo an IFL(s). They will be asked for the observational arm of the non SLN cohort. (See figure 2)

The remaining patients will be informed about the study, they can decide on standard IFL (group A) or refuse any surgery of the groin(s) (group C) In 75% of cases that undergo SLN (group B) it will be possible to retrieve the SLN. In approximately 14,5% of women undergoing a SLN procedure a tumour positive node will be present. It is not expected that the change of a successful SLN procedure relates to the presence or absence of a positive groin node. We expect to find a positive SLN in 11% of cases undergoing a SLN procedure, a negative SLN in 64%, and an unsuccessful procedure in 25%. This corresponds to respectively 10.5%, 61.8% and 24.1% of all included patients.

Percentage failure of SLN or IFL is known for neither procedure in the recurrent setting. In the primary setting groin recurrence after negative IFL and after negative SLN are both about 3%.

Sample size for V2SLN is calculated based on a conservatively estimated groin recurrence rate of 3%, with a maximum additional groin failure rate of SLN in local recurrent vulvar SCC of 5%. The sample size, considering an alpha of 0.10 and a beta of 0.20, is then calculated to be 150 patients with a first vulvar cancer recurrence undergoing a SLN procedure (group B) and a negative SLN (Figure 2) So, we expect that approximately 243 women with a 1st recurrence of vulvar cancer should be included in the study. Stopping rules with dynamic boundaries were constructed to guarantee the safety of the study by continuously monitoring the number of groin recurrences. See Appendix 1 for a detailed description of these stopping rules.

[figure not shown]

Figure 2 Flow diagram of calculation of sample size

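### Appendix 1 presents 150 as the calculated minimum size, but 150 was a program input and is not the minimum; it does meet the error limits, and its cut-off of 7 recurrences holds only down to 145 women

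*Protocol*

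**What the plan says.** Appendix 1 applies a predictive probability design and limits the type I and type II error to 0.10 each. On the size it states: "we calculated the minimum number of patients to obtain sufficient power with acceptable type I error rate". It then reports: "The results gave a sample size of 150 patients", with a lower stopping threshold of 0.001.

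The output printed below that text lists 150 as Nmax under its input data, beside the first look at 10 patients, the cohort size of 1 and the two success rates. The selection line reads "Parameter selection: Maximize Power" and is followed only by ranges for theta_L and theta_T. No other sample size appears. The attained errors at the end are alpha 0.0805 and beta 0.0840.

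Section 4.4 gives the same 150 but with beta 0.20, and converts it into inclusions: "So, we expect that approximately 243 women with a 1st recurrence of vulvar cancer should be included in the study". Section 12.5 ends the study once 125 women have been successfully treated with an SLN procedure and followed for two years.

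**The concern.** A minimum is a claim about the sizes below it, and the printed run tests none of them. Both attained errors also lie below 0.10, which suggests that a smaller size might do.

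Two things are at stake. First, the protocol misstates the basis of the number that drives recruitment, in a disease whose low incidence is its reason for a cohort design. Second, the success cut-off belongs to a particular number of evaluable women. Someone who takes 150 with at most 7 recurrences as the only design on offer has no guidance if fewer women have a 24-month outcome. Carrying the 7 over unchanged would then raise the type I error, that is, the chance of accepting a procedure with an 8% failure rate.

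**Working it through.** **Inputs, all from the Appendix 1 program output.** p0 = 0.92, p1 = 0.97 (failure rates 8% and 3%); Beta(0.8, 0.2) prior on the success rate ("0.8000 Prior a0"); looks as described in "we calculate PP continuously after 10 patients (i.e., with cohort size of 1"; theta_L = 0.001; theta_U = 1; theta_T searched from 0.80 to 0.95; limits alpha ≤ 0.10 and power ≥ 0.90.

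**Method.** After n women with s successes, the predictive probability of ending with at least r successes out of N is a beta-binomial tail with parameters 0.8 + s and 0.2 + n − s over the remaining N − n women. The trial stops if it falls below 0.001. Alpha and power are the probabilities of reaching N with at least r successes under 0.92 and 0.97, by exact recursion.

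**Step 1: reproduce the plan.** For N = 150 with success at ≥ 143 (at most 7 recurrences), alpha is 0.0805 and power 0.9160, equal to the printed values.

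**Step 2: read the printed tables.** From patient 60 onward the boundary is always 8 recurrences (60 − 52 = 8; 150 − 142 = 8). The printed probability of continuing at row n is therefore the chance of ending a trial of n women with at most 7 recurrences under that boundary.

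| Row | Continue, null case | Continue, alternative case |
|---|---|---|
| 149 | 0.0838 | 0.9184 |
| 145 | 0.0986 | 0.9277 |
| 144 | 0.1026 | 0.9299 |
| 125 | 0.2079 | 0.9639 |

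The protocol's own output thus shows both limits met from 145 upward, and alpha exceeded at 144.

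**Step 3: recompute with N itself as the maximum.** Early boundaries shift slightly, hence the small differences from step 2.

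| N | Recurrences allowed | Alpha | Power | Both limits met |
|---|---|---|---|---|
| 150 | 7 | 0.0805 | 0.9160 | yes |
| 149 | 7 | 0.0838 | 0.9185 | yes |
| 145 | 7 | 0.0986 | 0.9278 | yes |
| 144 | 7 | 0.1027 | 0.9301 | no |
| 144 | 6 | 0.0524 | 0.8560 | no |
| 131 | 6 | 0.0931 | 0.8993 | no |
| 130 | 6 | 0.0971 | 0.9023 | yes |
| 129 | 6 | 0.1013 | 0.9052 | no |
| 129 | 5 | 0.0490 | 0.8073 | no |
| 125 | 7 | 0.2086 | 0.9644 | no |
| 125 | 6 | 0.1196 | 0.9164 | no |
| 125 | 5 | 0.0594 | 0.8253 | no |

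Sizes 146 to 148 also pass with at most 7. No size below 130 passes, and none from 131 to 144.

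**Step 4: check without interim looks.** With X the number of recurrences, alpha = P(X ≤ c | N, 0.08) and power = P(X ≤ c | N, 0.03). For N = 130, c = 6 this gives 0.0973 and 0.9027; for N = 145, c = 7 it gives 0.0989 and 0.9283. The qualifying sizes up to 150 are the same.

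**Step 5: inclusions.** At the 61.8% SLN-negative share in section 4.4, 150 / 0.618 = 242.7, which is the stated 243.

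**The case against.** The chosen design does what it promises. At 150 women both errors are below 0.10 and both are printed, so no boundary or operating characteristic is wrong. That stands, and it limits the point to a false description of how the size arose and the missing link between cut-off and evaluable number.

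The printed run may also be the last of several with different Nmax. That is possible, and the documents do not say how 150 was reached. It would not make 150 the minimum, since 149 already qualifies.

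A reader might infer that the trial is 20 women too large and should be sized at 130. The figures do not support that. The size 130 is a sawtooth point: one woman fewer fails on alpha, one more fails on power, and passing resumes only at 145. It also depends on theta_L = 0.001; at the next grid step, 0.006, power at 130 is 0.8988, while 150 still passes (0.912). Nor can up to 20 losses from 150 be absorbed: losses of 6 to 19 leave a size with no qualifying cut-off. Only 5 can be lost with every intermediate size still meeting both limits.

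A reader might also conclude that 243 is wrong. It is a forecast of inclusions, correct for 150, and section 4.4 does not call it a minimum.

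**Conclusion.** The statement that 150 is the calculated minimum is false. Taking 145 as the start of the unbroken run of qualifying sizes up to 150, it is 5 women too high (150 − 145); the isolated size 130 also qualifies but is not a sound target. The trial is not underpowered at 150.

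The consequence worth acting on is the cut-off. At most 7 recurrences is valid under alpha ≤ 0.10 only with at least 145 evaluable women. At the 125 in section 12.5, read as 125 SLN-negative women, it would give alpha 0.209, and no cut-off there meets both limits. If the 125 includes SLN-positive women, the evaluable number is smaller still.

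This rests on the Appendix 1 settings, including beta 0.10. Under the beta of 0.20 in section 4.4 the smallest qualifying size is 98 (at most 4 recurrences, alpha 0.0994, power 0.8277), so 150 is not a minimum there either. The correction is worth making because it is cheap and bears on the final conclusion.

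**What to change.** In Appendix 1, replace the two sentences on the minimum and the resulting size with: *A maximum of 150 SLN-negative women was chosen; with success at no more than 7 recurrences the attained alpha is 0.0805 and the power 0.9160. The same limits are met at every size from 145 to 150.*

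Add that the cut-off of 7 applies only with at least 145 evaluable women. For smaller numbers, prespecify the lower cut-off that keeps alpha at or below 0.10 and print the attained power. Examples are at most 6 for 130 to 144 women (power 0.902 falling to 0.856) and at most 5 for 125 women (power 0.825).

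State one value of beta in section 4.4 and Appendix 1, and reconcile the 125 in section 12.5 with the 150. Leave the 243 as it is if 150 is kept. Do not adopt 130 as a target.

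The cost is re-running the program and adding a short table, with no extra patients. The downside is that the protocol must then state openly that power falls below 0.90 at every size from 131 to 144 and at every size below 130.
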